5.1.9 Premature discontinuation of ponesimod

The decision to prematurely discontinue study treatment may be made by the subject, the investigator or Actelion.

A subject has the right to prematurely discontinue study treatment at any time by withdrawal from treatment only or by withdrawal from treatment and any further participation in the study.

The investigator should discontinue study treatment for a given subject if, on balance, he/she believes that continued administration would be contrary to the best interests of the subject.

Premature discontinuation of study treatment may also result from a decision by Actelion, e.g., in case of premature termination or suspension of the study [see Section 9.3].

The main reason and whether discontinuation of study treatment is the decision of the subject, the investigator or Actelion must be documented in the eCRF.

A subject who prematurely discontinues study treatment is NOT considered as withdrawn from the study and will be followed up until the end of the safety follow-up period (30 days after study drug discontinuation), provided that the subject's consent for this limited participation in the study has not been withdrawn.

A subject who prematurely discontinues study treatment and withdraws consent to participate in any further study assessments is considered withdrawn from the study. Subjects who die or are lost to follow-up are also considered as withdrawn from the study. Withdrawal from the study and follow-up medical care of subjects withdrawn from the study is described in Sections 9.2 and 9.4, respectively.

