The visit window for this visit is \pm 7 days. The date of drug dispensing, preferably corresponding to the date of registration of the visit in the IRT system defines the date of the visit. Spirometry, DLco, OCT, ophthalmological examination, hematology, blood chemistry, urinalysis, spirometry, DLco and pregnancy tests may be performed up to 7 days prior to or after this visit date. The visits include:

- Administer Chronic GVHD Activity Assessment - Patient self-report [Appendix 7 – Form B]
- Administer LSS (subject completes the questionnaire after patient self-report but prior to any clinical assessments or interaction with health care providers, preferably while waiting for their appointment)
- Recording of changes in concomitant medications
- Assessing the MOC and recording in the eCRF (for WOCBP only)
- SBP/DBP (pre-dose)
- 12-lead ECG (pre-dose)
- Physical examination
- Spirometry (pre-dose; under the responsibility of the pulmonologist)
- DLco (pre-dose; under the responsibility of the pulmonologist)
- OCT (under the responsibility of the ophthalmologist)
- Ophthalmological examination (under the responsibility of the ophthalmologist)
- Hematology, blood chemistry (pre-dose)
- PK sampling (pre-dose and 3 hours post-dose)
- PD sampling (pre-dose and 3 hours post-dose)
- Urinalysis
- Urine pregnancy test for WOCBP
- Chronic GVHD Activity Assessments – physician-assessed [Appendix 7 – Form A]
- Recording of AEs and SAEs
- Study medication accountability and compliance review

- IRT call and study drug dispensing
- Remind WOCBP to use the MOC defined for this study. The reminders must be documented in the hospital chart.
- Schedule an appointment for next visit and instruct subject to:
 - bring back any bottles or blister wallets
 - not take study treatment on the day of study visit prior to coming to the site

8.2.5 Visits 6 and 7 - Weeks 16 and 20

The visit window for these visits is \pm 7 days. The date of drug dispensing, preferably corresponding to the date of registration of the visit in the IRT system defines the date of the visit. Hematology, blood chemistry, urinalysis and pregnancy tests may be performed up to 7 days prior to or after this visit date. The visits include:

- Recording of changes in concomitant medications
- Assessing and recording of MOC (for WOCBP)
- SBP/DBP (pre-dose)
- 12-lead ECG (pre-dose)
- Hematology, blood chemistry (pre-dose)
- PK sampling (pre-dose)
- PD sampling (pre-dose)
- Urinalysis

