11.1.3 Per-protocol set

The Per-protocol set (PPS) is defined as subjects from the FAS without any major protocol deviations. The most important protocol deviations include:

- Subject failing to reach the Week 24 assessment, i.e., by discontinuing treatment early or for any other reason than lack of efficacy or death
- Subject withdrawing consent before the Week 24 assessment

Confidential

- Subjects not adhering to the treatment regimen (mandatory concomitant medication, up-titration, study drug)
- Subject receiving prohibited concomitant therapy
- Start of any other IS systemic therapies during the course of the trial

Additional details of the definition of the PPS will be described in the SAP.

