- Partial or complete organ-specific response for the specific organ manifestation at Week 12 and Week 24 in subjects with a specific organ manifestation of chronic GVHD
 - Affected organs limited to 2014 NIH consensus criteria organs of skin, eyes, mouth, esophagus, upper GI, lower GI, liver, lungs, and joints and fascia

This endpoint is a binary sub-endpoint of the first exploratory endpoint (see above), split by organ. The endpoint will be derived in the same way as described above but at an organ level. The endpoint will be evaluated independently at the Week 12 and Week 24 assessment. Only organs with reversible manifestations will be included in the analysis.

Confidential

Only subjects with manifestations at baseline or subjects developing manifestations during the study at the corresponding organ will be included in the analyses of the sub-endpoints. Patients who discontinue the study prior to the Week 24 assessment are considered non-responders.

- Partial or complete overall response at Week 12

This binary endpoint is defined like the first exploratory endpoint (see above) but at the Week 12 assessment.

- Complete response at 24 weeks

A responder of this binary endpoint is defined as reaching a complete response at the Week 24 assessment. A non-responder is defined as reaching a partial or mixed response or no response (stable disease or progression) at the Week 24 assessment or dropping out of the study prior to the Week 24 assessment.

- Partial or complete overall response at latest evaluable assessment during the core study (Week 12 and Week 24)
- Average glucocorticoid daily dose over 24 weeks versus baseline dose

The average dose is defined as the sum of all doses of glucocorticoid received, adjusted by the time in days.

- Percent glucocorticoid dose at Week 24 versus baseline.

This exploratory endpoint is defined as the percentage of the glucocorticoid dose received at the Week 24 assessment compared to the dose received at baseline.

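### The dropout rule for organ-specific response (Section 11.2.3) is tied only to Week 24, so read literally it turns observed Week 12 organ responders who leave later into Week 12 non-responders

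*Combined protocol and SAP*

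**What the plan says.** Section 11.2.3 introduces the endpoint in these words, with the name of the disease cut short here: "Partial or complete organ-specific response for the specific organ manifestation at Week 12 and Week 24 in subjects with a specific organ manifestation of chronic". Its definition then makes two statements about timing:

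- On the visits: "The endpoint will be evaluated independently at the Week 12 and Week 24 assessment".
- On dropout, as the closing sentence: "Patients who discontinue the study prior to the Week 24 assessment are considered non-responders".

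No separate Week 12 dropout rule is given. The same closing sentence also ends the definitions of Week 24 overall response and of rescue therapy in Section 11.2.3. Sections 6.3.3 and 6.3.4, which introduce the efficacy endpoints, state no such rule.

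Two neighbouring endpoints are handled differently. For overall response at Week 12: "This binary endpoint is defined like the first exploratory endpoint (see above) but at the Week 12 assessment". A further endpoint is "Partial or complete overall response at latest evaluable assessment during the core study (Week 12 and Week 24"); it covers overall response only, not response by organ.

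Week 12 organ data are collected. The Visit 5 (Week 12) list in Section 8.2.4 includes "Chronic GVHD Activity Assessments – physician-assessed [Appendix 7 – Form A".

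**The concern.** A rule that scores a missing assessment as a failure is a common conservative choice. Here, taken at its word, it reaches back over an assessment that was made. A subject who responds in an organ at Week 12 and leaves at Week 20 has a recorded Week 12 result, yet falls under the rule and would be tabulated as a Week 12 non-responder. Later departure can then only lower the Week 12 organ rate, and the two visits are no longer evaluated separately as the paragraph requires.

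At stake is the early organ-level signal in a small single-arm study. Organ-specific tables have denominators below the enrolled number unless every subject has that organ involved, so one or two recoded subjects can change a displayed rate visibly.

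**Working it through.** **Figures the plan gives.** It states no response rate, sample size or dropout figure for organ response. Its power figures concern the lymphocyte test and are not used here. The relevant input is the general dropout allowance:

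- Section 11.4.1: 30 subjects, 25% dropout, 23 reaching Week 12. Check: 30 × 0.75 = 22.5, rounded up to 23, so 30 − 23 = 7 leavers.
- Section 11.4.2: up to 25% dropping out over the Core Treatment Period, with no split before and after Week 12.

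Let k be the number leaving between the Week 12 and Week 24 assessments. Under the Section 11.4.1 scenario the seven have gone before Week 12. They are Week 12 non-responders under either reading of the rule, so they contribute nothing to k. Under Section 11.4.2, k could be anything from 0 to 7. That range is an assumption.

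**Formula.** With n subjects evaluable for the organ and r Week 12 responders among the k leavers, the literal rule lowers the reported Week 12 rate by r/n. If leavers respond at the same rate p as everyone else, r = p × k and the loss is p × k / n. If every leaver had responded, the loss is k / n.

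**Results for n = 30 and p = 0.50 (both assumed).**

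| k | Loss, leaving unrelated to response | Reported rate | Loss, all leavers responders |
|---|---|---|---|
| 0 | 0 | 50.0% | 0 |
| 2 | 0.50 × 2/30 = 3.3 points | 46.7% | 2/30 = 6.7 points |
| 4 | 0.50 × 4/30 = 6.7 points | 43.3% | 4/30 = 13.3 points |
| 7 | 0.50 × 7/30 = 11.7 points | 38.3% | 7/30 = 23.3 points |

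**Other response rates, k = 7.** At p = 0.20 the loss is 0.20 × 7/30 = 4.7 points; at p = 0.75 it is 0.75 × 7/30 = 17.5 points.

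**Smaller organ groups.** Taking n = 30 supposes that all 30 subjects have the organ involved. With 10 involved (assumed), each Week 12 responder who leaves later costs 1/10 = 10 points.

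**With a rule keyed to the visit.** The Week 12 loss due to later leavers is 0 for every k.

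**Whether another analysis recovers these responders.** The latest-evaluable endpoint keeps Week 12 data but is not broken down by organ. The per-protocol set does not recover them either, because Section 11.1.3 treats as a major deviation "Subject failing to reach the Week 24 assessment, i.e., by discontinuing treatment early or for any other reason than lack of efficacy or death"; most such subjects are removed from that set altogether.

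**The case against.** The strongest reply is that the sponsor probably did not intend this. The sentence calling for independent evaluation points the other way, and the dropout sentence repeats one written for endpoints read only at Week 24. It may have been meant for the Week 24 evaluation alone. Section 11 also leaves derivation algorithms to the statistical analysis plan, and no separate text of that plan is in the document reviewed, so a correction there cannot be ruled out. This stands as a limit: the text conflicts with itself, and it is not certain that Week 12 responses would be recoded. It does not remove the point, because the only rule stated gives the wrong Week 12 result when followed.

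Three stronger readings are tempting, and the documents do not support them.

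- A reader might infer that overall response at Week 12 carries the same defect. Its definition moves the first endpoint to the Week 12 assessment, and the natural reading is that the dropout clause moves with it.
- A reader might multiply a Week 12 rate by 0.75, for example 40% falling to 30%. That places the whole 25% after Week 12, whereas Section 11.4.1 pairs the 25% with 23 subjects reaching Week 12. The 40% is not in the documents either.
- A reader might conclude that the two visits can no longer be compared at all, or that the study's main conclusion is affected. No test or formal comparison of organ response between visits is planned, Section 11 says all data will be listed, and the primary analysis concerns lymphocyte counts.

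**Conclusion.** The point holds for organ-specific response. As written, the rule counts an observed Week 12 organ responder who leaves before the Week 24 assessment as a Week 12 non-responder in the FAS. The bias is downward whenever such a subject exists and is otherwise zero. The loss is 0 to 11.7 percentage points if n = 30, Week 12 response is 50% and unrelated to leaving, and 0 to 7 subjects leave between the visits. It reaches 23.3 points only if all seven had responded. The number of leavers and the response rate are assumptions.

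It is also unclear who the rule covers. Section 5.1.9 states: "A subject who prematurely discontinues study treatment is NOT considered as withdrawn from the study". Yet under Section 3.2.3 a subject who stops the drug early has the end-of-study visit 30 days after the last dose, so stopping at Week 16 ends follow-up at about Week 20. The plan does not say whether that counts as discontinuing the study.

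Importance is modest. The endpoint is exploratory and descriptive, and the primary pharmacodynamic analysis, its error rate and the sample size are untouched. It is still worth correcting, because the stated rule discards observed data and no other planned summary restores them by organ.

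**What to change.** Replace the closing sentence of the organ-specific definition in Section 11.2.3 with a rule keyed to the visit. A subject who discontinues before the Week 12 assessment is a non-responder at Week 12. One who discontinues before the Week 24 assessment is a non-responder at Week 24, and any Week 12 result already observed stands.

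Two small additions would close the remaining gaps:

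- State whether a subject who stopped the drug early and had the end-of-study visit before Week 24 counts as having discontinued the study for this rule.
- Confirm in a few words that the dropout clause for overall response at Week 12 refers to the Week 12 assessment.

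Section 11.2.5 carries the core definitions into the Extension Treatment Period, and Section 11.2.9 reads organ response there at Weeks 12, 24 and 96. The visit-keyed wording should apply there too.

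The cost is one replaced sentence and two clarifications, with no new data, visits or subjects. If a separate statistical analysis plan already states the rule by visit, Section 11.2.3 only needs to be brought into line with it.

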4.3 Inclusion criteria

For inclusion into the study, all of the following inclusion criteria must be fulfilled. No waivers of any of the criteria for any subject are allowed:

1. Signed informed consent prior to initiation of any study-mandated procedure.

Confidential

2. Males and females aged 18 to 70 years.
3. Recipients of allogeneic HSCT diagnosed with chronic GVHD.
4. Currently receiving systemic IS therapy at enrollment, with no dose changes in the 14 days prior to enrollment, consisting of systemic glucocorticoids AND/OR one of the following systemic agents: cyclosporine (CsA), tacrolimus (TAC), mycophenolate mofetil (MMF), mycophenolate sodium (MPS), everolimus (EVL), sirolimus (SRL), or methotrexate (MTX).
5. Subject needs a change of current systemic IS therapy, in the opinion of the investigator, based on all of the following conditions:
 - a. Symptomatic moderate or severe chronic GVHD per NIH global severity scoring assessed at screening [see Appendix 2 for NIH global severity scoring form].
 - b. Glucocorticoid refractory, dependent, or intolerant status at screening [see Appendix 1 for guidance].
 - c. Evidence of GVHD progression at enrollment despite \geq 4 weeks current systemic IS therapy, OR without evidence of GVHD improvement at enrollment despite \geq 8 weeks current systemic IS therapy. Current systemic IS therapy must be the same as in inclusion criterion 4 [see Appendix 1 for guidance].
6. Chronic GVHD manifestations involve at least one of the following organs: skin, mouth, eyes, joints and fascia, esophagus, upper or lower GI tract. The qualifying manifestation should have an NIH chronic GVHD activity assessment score of at least 1 at enrollment [see Form A, Appendix 7].
7. WOCBP, as defined in Section 4.3.1, must have a negative serum pregnancy test at screening and a negative urine or serum pregnancy test prior to enrollment, and must agree to undertake urine pregnancy tests every 4 weeks during the study and up to the protocol defined EOS.
8. WOCBP must agree to use acceptable MOC during the study and up to the protocol defined EOS.

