5.2.2 Modifications to IS treatments

Mandatory and allowed (e.g., topical IS) IS therapies make up the subject's background chronic GVHD IS therapy during the study. The dose and frequency of these medications should be kept constant during the study.

Systemic glucocorticoids

Glucocorticoid dosing should not be increased or decreased during the course of the study, with the following exceptions:

- The investigator may see reason to initiate or increase the dose of systemic glucocorticoid to treat chronic GVHD flare or another condition. In this case, the investigator should consult with the sponsor prior to initiation or dose increase and the

Confidential

reason for dose increase should be documented. The subject may continue on ponesimod. The prednisone equivalent dose should never exceed 1 mg/kg/day.

- Systemic glucocorticoid dosing may be lowered to avoid or prevent short- and long-term glucocorticoid toxicity. For subjects on longer term glucocorticoid therapy, it is recommended that the dose reduction rate does not exceed 10% of dose per week. Glucocorticoid dosing may be increased following reduction, if medically indicated.
- Systemic glucocorticoid dosing is not subject to restrictions during the Extension Treatment Period.

Mandatory systemic IS other than ponesimod or systemic glucocorticoids

Systemic IS dosing (mg daily dose) should not be increased above baseline dose during the course of the study, with the following exception:

- Systemic IS blood or serum level is below the therapeutic range that was defined for the subject at the time of entry into the study. The dose should be increased to restore blood or serum levels to within the defined therapeutic range. (ISs that are not monitored with blood or serum level monitoring may never be increased above baseline dose.)

Systemic IS dosing (mg daily dose) should not be lowered during the course of the study, with the following exceptions:

- AE or intolerance due to the systemic IS. The dose should be sufficiently lowered or discontinued, per investigator judgment.
- Systemic IS blood or serum level is above the therapeutic range that was defined for the subject at the time of entry into the study. The dose should be lowered to restore blood or serum levels to within the defined therapeutic range.

Topical CNIs or glucocorticoids

- The sponsor recommends not starting or increasing dosage of topical CNI or topical glucocorticoid therapy during the course of the core study.

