11 STATISTICAL METHODS

All statistical analyses will be conducted by Actelion or by designated contract research organizations supervised by Actelion.

The Statistical Analysis Plan (SAP) will be approved prior to database lock for the final analyses. The SAP provides the full details of all analyses, data displays, and algorithms to be used for data derivations.

All data will be listed, and endpoints will be summarized by appropriate descriptive statistics (tables or figures), typically including:

- Number of non-missing observations, number of missing observations, mean, standard deviation (STD), median, Q1, Q3, minimum and maximum for continuous endpoints;
- Number of non-missing observations, number of missing observations and frequency with percentage per category (percentages based on the number of non-missing observations) for categorical endpoints;
- Number of subjects at risk, cumulative number of events, cumulative number of censored observations and Kaplan-Meier estimates of the survival function for time-to-event endpoints.

Absolute changes from baseline are defined as: post-baseline value minus baseline value, i.e., a positive sign indicates an increase as compared to baseline.

A percentage (relative) change from baseline is defined as the absolute change from baseline divided by the baseline value (if the baseline value not equal 0) multiplied by 100.

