11.2.8 Analysis of the efficacy variables

The analyses of all exploratory endpoints will be based on the PPS and FAS, if applicable. The following binary endpoints will be summarized descriptively as described in Section 11:

- Achievement of a partial or complete overall response at 24 weeks (per NIH Consensus Development Project response criteria)
- Need for rescue therapy for chronic GVHD
- Partial or complete organ-specific response for the specific organ manifestation at Week 12 and Week 24 in subjects with a specific organ manifestation of chronic GVHD
- Partial or complete overall response at Week 12
- Complete response at Week 24
- Partial or complete overall response at latest evaluable assessment during the core study (Week 12 and Week 24)

The remaining two exposure-related, continuous endpoints will be analyzed based on summary statistics as described in Section 11:

- Average glucocorticoid daily dose over 24 weeks versus baseline dose
- Percent glucocorticoid dose at Week 24 versus baseline

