15 APPENDICES

Appendix 1 Additional subject eligibility guidance

The following guidance should be applied by investigators in assessing the eligibility for subjects for enrollment in this study, with respect to inclusion criteria 5b and 5c.

Inclusion criterion 5b
The investigator must determine subject to be glucocorticoid refractory, dependent, or intolerant at screening.
Guidance

Systemic glucocorticoids are established first-line therapy for chronic GVHD. This study will not include subjects who could benefit from standard use of glucocorticoids. Therefore, a glucocorticoid refractory, dependent, or intolerant status must exist for all eligible subjects.
 
Currently, there are no uniformly accepted definitions for these states in chronic GVHD.
 
The investigator should consider the following definitions in his or her assessment of the subject's prior experience with glucocorticoids:
 
Refractory to or dependent on glucocorticoids
 
• Progression on prednisone-equivalent steroid dose at 1 mg/kg/day for 2 weeks• Stable disease on prednisone-equivalent steroid dose at ≥ 0.5 mg/kg/day for 4–8 weeks• Inability to taper below prednisone-equivalent steroid dose of 0.5 mg/kg/day• Treatment with prednisone-equivalent steroid dose of > 0.25 mg/kg/day received for ≥ 12 weeks 
Sources: [Wolff 2011b, Pai 2014, Inamoto 2014b]
 
Intolerant to glucocorticoids
 
• Subjects have a glucocorticoid intolerance that required a dose reduction. Intolerance includes the development of severe side effects due to glucocorticoid use, such as poorly controlled hypertension or diabetes, active peptic ulcer disease, myopathy, psychiatric derangements, significant bone loss, or systemic fungal infection.

Inclusion criterion 5c
Subjects have evidence of GVHD progression at enrollment despite \geq 4 weeks current systemic IS therapy, OR are without evidence of GVHD improvement at enrollment despite \geq 8 weeks current systemic IS therapy. Current systemic IS therapy must be same as in inclusion criterion 4.
Guidance

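### The Week 24 glucocorticoid percentage has no value for subjects on no systemic steroid at baseline, so any of them who start steroids on study are left out of the summary

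*Combined protocol and SAP*

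**What the plan says.** Section 11.2.3 lists two steroid-dose endpoints. The last is the Week 24 percentage, "defined as the percentage of the glucocorticoid dose received at the Week 24 assessment compared to the dose received at baseline". The other sets the average daily dose over 24 weeks against the baseline dose: "The average dose is defined as the sum of all doses of glucocorticoid received, adjusted by the time in days". The section does not say whether that comparison is a ratio or a difference. Section 11.2.8 gives the method for both: "The remaining two exposure-related, continuous endpoints will be analyzed based on summary statistics as described in Section 11".

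Three other places bear on the denominator:

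- **Section 4.3, criterion 4.** Current systemic therapy at entry is described as "consisting of systemic glucocorticoids AND/OR one of the following systemic agents", followed by seven non-steroid drugs. Section 5.2.1 repeats the same and/or rule for treatment on study.
- **Section 5.2.2.** "The investigator may see reason to initiate or increase the dose of systemic glucocorticoid to treat chronic GVHD flare or another condition". The sponsor is to be consulted first, and "The subject may continue on ponesimod".
- **Section 11, general definitions.** A percentage change is the absolute change "divided by the baseline value (if the baseline value not equal 0) multiplied by 100". Nothing is said about what to report when the baseline is zero.

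**The concern.** A subject who enters on a non-steroid agent alone has a baseline steroid dose of zero. Such subjects are foreseeable, because steroid-intolerant subjects are eligible. Appendix 1 describes them: "Subjects have a glucocorticoid intolerance that required a dose reduction". The guidance does not say how far the dose was reduced, so intolerance is a plausible source of zero or low baselines, not proof of them.

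If one of these subjects flares and is put on a steroid, that is a steroid outcome the endpoint ought to reflect. The definition gives no value for it. A zero-baseline subject can only stay at zero or go up, so the only dose movement that can be lost from this group is an increase. A reader who sees a mean Week 24 percentage below 100 could take it to describe the whole study population when it describes baseline steroid users only. The same structure carries into the extension. Section 11.2.9 compares both endpoints with visit EX-1, and Section 5.2.2 lifts the restrictions on systemic steroid dosing in that period.

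**Working it through.** The plan states no figure for this endpoint, so there is none to reproduce. The check applies the definition directly.

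**Definition at zero.** Percentage = 100 × (Week 24 dose) / (baseline dose).

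- 0.5 to 0.25 mg/kg/day: 100 × 0.25/0.5 = 50%.
- 0 to 0: undefined.
- 0 to 0.5: undefined.

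A subject who stayed off steroids and a subject who started them therefore look the same: neither has a value.

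**Effect on the summary.** Inputs: N = 30 (Section 11.4.1). Everything else is assumed, because the documents do not give it: m subjects at zero baseline (3 to 12), a of them starting (none to two thirds), baseline dose in users b = 0.5 mg/kg/day, started dose s = 0.5 mg/kg/day, and every user with the same ratio r of Week 24 to baseline dose. Let k = 30 − m.

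- Reported mean percentage = 100 × r
- Total-dose ratio, all 30 = 100 × (k·b·r + a·s)/(k·b)
- Gap = 100 × a·s/(k·b), which is 100 × a/k when s = b
- Mean change in users = b·(r − 1)
- Mean change in all 30 = [k·b·(r − 1) + a·s]/30

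With users tapering by 20% (r = 0.8):

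| Zero baseline (m) | Starters (a) | Reported mean % | All-subject total-dose ratio % | Mean change, users (mg/kg/day) | Mean change, all 30 (mg/kg/day) |
|---|---|---|---|---|---|
| 3 | 0 | 80 | 80.0 | −0.100 | −0.090 |
| 3 | 1 | 80 | 83.7 | −0.100 | −0.073 |
| 6 | 2 | 80 | 88.3 | −0.100 | −0.047 |
| 9 | 6 | 80 | 108.6 | −0.100 | +0.030 |
| 12 | 8 | 80 | 124.4 | −0.100 | +0.073 |

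Third row in full: (24 × 0.5 × 0.8 + 2 × 0.5)/(24 × 0.5) = 10.6/12 = 88.3%; mean change (24 × (−0.1) + 2 × 0.5)/30 = −1.4/30 = −0.047.

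The gap does not depend on r. Across the scenarios with at least one starter it runs from 1/27 = 3.7 to 8/18 = 44.4 percentage points. With no starter it is 0.

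**Where the direction is not fixed.** The result above concerns total dose. Two other scales can behave differently.

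- *Mean of individual percentages.* Assume 19 users go from 0.4 to 0.3 (75% each), one goes from 0.05 to 0.5 (1000%), and 10 are at zero, of whom 2 start 0.2. The reported mean is (19 × 75 + 1000)/20 = 121%. Total dose over all 30 goes from 19 × 0.4 + 0.05 = 7.65 to 19 × 0.3 + 0.5 + 2 × 0.2 = 6.6, which is 86%. Here the reported mean overstates steroid use although two starters are missing from it.
- *Mean absolute change.* If users' doses rise 20% and 3 zero-baseline subjects all stay at zero, users show +0.100 and all 30 show 27 × 0.1/30 = +0.090 mg/kg/day, so the users-only figure is the less favourable one.

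**The case against.** The strongest reply is that this is a minor derivation detail in a descriptive analysis, and that other outputs would reveal the starters. Taking its parts in turn:

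- **The effect may be nil.** True if no zero-baseline subject is on steroid at Week 24. Dose increases for flare in baseline users are also counted, as values above 100%.
- **Always favourable.** A reader might infer that the endpoint always errs towards steroid sparing. The documents do not support that. The one-directional result holds on the total-dose scale and needs at least one starter. As the 121% against 86% example shows, a mean of individual percentages can err the other way, and Section 11 also calls for the median and quartiles.
- **Section 11 excludes these subjects.** A reader might infer this from its non-zero condition. That rule covers percentage change, whereas this endpoint is a percentage of baseline. The value is missing because of the arithmetic, not because of an exclusion rule.
- **Missing counts are shown and all data listed.** So the reduced n would be visible. But a missing count does not separate a subject who stayed off steroids from one who started, or from one with no Week 24 data.
- **Starts are counted elsewhere.** The 24-week average is itself defined at zero baseline and includes doses started on study. It fails in the same way only if its comparison with baseline is a ratio, which is not stated. The rescue endpoint in Section 11.2.3 includes adding new systemic immunosuppression, but it also gives steroids their own threshold of more than 1 mg/kg/day, so whether a new steroid counts is unclear. Section 5.1.10 stops ponesimod before rescue immunosuppression in the Core period, while Section 5.2.2 lets a steroid starter continue; these passages must be reconciled. It therefore cannot be said that starts are never captured, only that capture is uncertain.
- **The SAP may settle it.** Section 11 leaves derivation algorithms to the SAP. No zero-baseline rule appears in the text reviewed.

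These points limit the size and the wording. They do not supply a value for the omitted subjects.

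**Conclusion.** The point holds in limited form. The percentage is undefined for subjects with no baseline steroid. They are eligible, and they may start steroids on study while continuing ponesimod. On the total-dose scale the summary then understates Week 24 steroid use relative to all subjects whenever one of them is on steroid at Week 24. The size is unknown; the 3.7 to 44.4 point range rests wholly on assumed shares, starting rates and doses. For baseline users taken alone, the omission causes no bias.

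The weight is modest. Efficacy is an exploratory objective (Section 2.2), steroid sparing is not named as an objective, no test is planned on this endpoint, and neither the primary lymphocyte analysis nor the sample size depends on it. It should still be corrected, because a better summary can be built from data already collected.

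**What to change.** In Section 11.2.3 and the SAP:

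1. Make absolute change in prednisone-equivalent dose (mg/kg/day) the main summary, both as Week 24 minus baseline and as 24-week average minus baseline, in all FAS subjects with data, including those at zero baseline. This also settles whether the average-dose comparison is a ratio or a difference.
2. Keep the percentage as a supplement labelled as restricted to subjects on systemic steroid at baseline.
3. Report the number of subjects at zero baseline and how many of them started steroids.
4. State whether a new systemic steroid at or below 1 mg/kg/day counts as rescue therapy for the rescue endpoint.
5. Apply items 1 to 3 to the extension versions in Section 11.2.9, with EX-1 as baseline.

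The cost is SAP wording and a small extra table. Dose, frequency and dates of concomitant therapy are already recorded (Section 5.3.3), and weight is measured at Day 1 and EOT1 (Sections 8.1.2.1 and 8.2.6). Section 11 has the SAP approved before database lock, which is the time to make the change. The downside is that the steroid-sparing figure may look less favourable.
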